At designated study visits during the 24-month Treatment Period, blood samples will be collected for clinical safety labs, including vitamin D levels. In addition, blood samples will be collected for assay of serum estradiol, plasma concentrations of elagolix and norethindrone.

BMD will be assessed throughout the Treatment Period. Following baseline, DXA scans will be obtained at Treatment Months 6, 12, 18 and 24. A DXA scan will be required if a subject discontinues at the time of or after the Treatment Month 6 visit or if the reason for premature discontinuation is due to the occurrence of a fracture or any newly diagnosed bone condition.

Vital signs assessments will be conducted at all on-site study visits. Additional safety assessments are completed as appropriate at designated study visits throughout the Treatment Period. Adverse event and concomitant medication review will be conducted at all Treatment Period study visits.

Criteria for Assessment of Subject Status Following the Open-Label Run-In Period:

At the Treatment Month 3 study visit, subjects will be assessed as either an 'efficacy responder' or an 'incomplete efficacy responder' based on responses entered in the e-Diary on the Daily Diary endometriosis-associated pain score via NRS. The status of a subject will be determined within the e-Diary system as follows:

- Efficacy responder: $\geq 30\%$ decrease (improvement) from Baseline based on the average of the Daily Diary for endometriosis-associated pain score via NRS over a 35 day window
- Incomplete efficacy responder: $< 30\%$ decrease (improvement) from Baseline based on the average of the Daily Diary for endometriosis-associated pain score via NRS over a 35 day window
- Following conclusion of the Open-Label Run-In Period, treatment arm assignment for all subjects will become and remain blinded for the remainder of the 24-month Treatment Period. The assessment of responder status is also blinded.

At the Treatment Month 3 study visit, any subjects that have zero entries for the Daily Diary for endometriosis-associated pain score via NRS during the 35 day window prior to the study visit will continue dosing with 150 mg QD for the remainder of the treatment period (will be assigned to Group A).

Dose Escalation During the Treatment Period:

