Subjects assessed as "efficacy responders" (as defined above) will be assigned to continue dosing with elagolix 150 mg QD (Group A) in a blinded manner via Interactive Response Technology (IRT). All other subjects assessed as "incomplete efficacy responders" will be assigned randomly (in an equal ratio) via IRT to either elagolix 150 mg QD (Group B) or elagolix 200 mg BID plus E2/NETA (1 mg/0.5 mg) QD (Group C) for 3 months. To preserve the blind, IRT will be utilized for study drug assignment for all subjects. The first dose from the newly assigned study drug kit at Treatment Month 3 will be administered at the site. The pharmacokinetic and pharmacodynamics samples must be obtained prior to study drug administration at the Treatment Month 3 visit.

At the Treatment Month 6 study visit, in a blinded manner via IRT, all subjects who were incomplete efficacy responders and randomly assigned at Treatment Month 3 to elagolix 150 mg QD will again be assessed for efficacy response in the same manner as was done at the Treatment Month 3 visit. All subjects in this group (Group B) who become efficacy responders will continue dosing with elagolix 150 mg QD in a blinded manner (Group E). All other subjects in this group who are assessed as incomplete efficacy responders at Month 6 will escalate dosing to elagolix 200 mg BID plus E2/NETA (1 mg/0.5 mg) QD (Group D). To preserve the blind, IRT will be utilized for treatment assignment of all subjects; however, only subjects randomly assigned at Treatment Month 3 to the elagolix 150 mg QD (Group B) will have a chance for dose modification. The first dose from the newly assigned study drug kit at Treatment Month 6 will be administered at the site. The pharmacokinetic and pharmacodynamics samples must be obtained prior to study drug administration at the Month 6 visit.

At the Treatment Month 6 study visit, any subjects that have zero entries for the Daily Diary for endometriosis-associated pain score via NRS during the 35 day window prior to the study visit will continue dosing on the current dose assignment for the remainder of the treatment period.

The treatment assignments following the Treatment Month 6 study visit will continue for all subjects for the duration of the 24-month Treatment Period in a blinded manner. There will not be further dose adjustments following the Treatment Month 6 visit for any subject.

BMD Assessment and Subject Specific Safety Stopping Criteria for BMD During the Treatment Period:

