If the results of any post-baseline DXA prior to and including Month 24, as read by the central imaging vendor selected for the study, document either of the following results, the subject must be discontinued from study drug dosing and will enter the Follow-Up Period:

- a Z-score (for subjects < 40 years of age at the time of the Screening DXA) or T-score (for subjects ≥ 40 years of age at the time of the Screening DXA) of < -2.5 in the lumbar spine, total hip or femoral neck, the subject OR
- a BMD decrease from baseline of $> 8\%$ in the lumbar spine, total hip or femoral neck.

A BMD decrease at any anatomic region (lumbar spine, total hip or femoral neck) that results in discontinuation from the study should be reported as an adverse event (Section 6.1.1).

DXA Scans Performed for Subjects Who Prematurely Discontinue in the Treatment Period

DXA scans are required to be performed as part of the Premature Discontinuation visit as follows:

- Subjects who discontinue prior to the Treatment Month 6 visit only if the reason for premature discontinuation is due to the occurrence of a fracture or any newly diagnosed bone condition
- Subjects who discontinue at the time of or after the Treatment Month 6 visit.

However, if a subject is being discontinued from the study due to a Z-score or T-score of < -2.5 in any region, or BMD decrease from baseline of $> 8\%$ in any region, additional

DXA scans do not need to be performed as a part of the Premature Discontinuation visit procedures. In these circumstances, the subject would enter the Follow-Up Period and continue with required BMD evaluations.

DXA Scans Performed in the Follow-Up Period

DXA scans of the lumbar spine, total hip, and femoral neck will be obtained at Follow-Up Months 6 and/or 12 for those subjects whose follow-up period visits occur prior to the study conclusion (i.e., approximately 30 days after the last completed Treatment Period visit).

Endometrial Biopsy

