5.3.4 Safety Variables

BMD Assessments:

BMD assessments will be summarized. Modifiable and non-modifiable risk factors will be assessed as they relate to baseline BMD and changes in BMD over time, including: smoking and alcohol use, physical activity (IPAQ), previous use of calcium and vitamin D, prior medications, race, age, height and weight (BMI), family history of fracture and family history of osteoporosis.

Other Safety Assessments:

Safety evaluations will also include physical examinations, AEs and concomitant medications, clinical laboratory tests and vital sign measurements. Endometrial health will be assessed via TVU and biopsy.

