8.1.5 Safety

8.1.5.1 General Considerations

All enrolled subjects who took at least one dose of the study drug will be included in the safety analyses.

Data collected during the 3 month Open-Label Run-In Period will be summarized for all subjects combined.

For safety data collected during Treatment Months 4 – 6, summaries will be presented for the following groups.

- Subjects who are responders to Elagolix 150 mg QD treatment group at Month 3 (Group A) and subjects who are incomplete responders to Elagolix

150 mg QD treatment group at Month 3 and randomized to Elagolix 150 mg QD treatment group at Month 3 (Group B) will be combined

- Subjects who are incomplete responders to Elagolix 150 mg QD treatment group at Month 3 and randomized to Elagolix 200 mg BID plus E2/NETA treatment group at Month 3 (Group C).

For safety data collected during Treatment Months 7 – 24, summaries will be presented for the following group.

- Subjects who are responders to Elagolix 150 mg QD treatment group at Month 3 (Group A) and subjects who are incomplete responders to Elagolix 150 mg QD treatment group at Month 3 and randomized to Elagolix 150 mg QD treatment group at Month 3 and are responders at Month 6 and continue to receive Elagolix 150 mg QD (Group E) will be combined.
- Subjects who are incomplete responders to Elagolix 150 mg QD treatment group at Month 3 and randomized to Elagolix 150 mg QD treatment group at Month 3 and are incomplete responders at Month 6 and are switched to Elagolix 200 mg BID plus E2/NETA (Group D).
- Subjects who are incomplete responders to Elagolix 150 mg QD treatment group at Month 3 and randomized Elagolix 200 mg BID plus E2/NETA treatment group at Month 3 (Group C).

Baseline for all subjects will refer to the data obtained prior to dosing on Day 1 of the Open-label Run-in Period.

In general, for continuous variables, descriptive statistics (mean, standard deviation, median, minimum and maximum) will be summarized by treatment group. Categorical data will be summarized with frequencies and percentages by treatment group. Unless otherwise specified, no statistical tests will be performed.

Analysis details will be specified in the SAP.

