8.1.5.2 Adverse Events

Adverse events (AEs) will be coded using the Medical Dictionary for Regulatory Activities (MedDRA) dictionary. Treatment-emergent adverse events (TEAEs) will be summarized. TEAEs are defined as AEs with a start date on or after the first dose of the study drug and within 30 days of the last dose of the study drug. AEs starting more than 30 days following discontinuation of the study drug will not be included in the summaries of TEAEs.

Frequencies and percentages of subjects with TEAEs will be calculated for each treatment group as follows:

- Any event
- By system organ class, and preferred term
- By system organ class, preferred term and maximum relationship
- By system organ class, preferred term and maximum severity
- Any event and by system organ class and preferred term for events resulting in study drug discontinuation
- Any event and by system organ class and preferred term for serious events
- Any event and preferred term for AESIs (e.g., hypoestrogenic adverse events)

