8.1.5.4 Bone Mineral Density

The key BMD evaluations are lumbar spine at Month 12 and Month 24. Secondary BMD endpoints include total hip and femoral neck.

The Z- and T-scores and BMD percent change from baseline values during the 24 month treatment period will be summarized. Factors associated with a change in BMD will be

explored. Unless otherwise specified, no statistical comparisons on BMD assessment will be performed between treatment groups.

Full analysis details will be provided in the SAP.

Post-treatment bone mineral density scans will be summarized similarly, as appropriate.

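### Months 4–6 safety data are to be shown as Groups A and B pooled beside Group C, so the randomized 150 mg arm (B) is never displayed next to its randomized comparator

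*Combined protocol and SAP*

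**What the plan says.** Section 8.1.5.1 fixes the safety groupings by period:

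- **Open-label run-in:** all subjects together.
- **Months 4–6:** two columns. Group A is merged with the incomplete responders "randomized to Elagolix 150 mg QD treatment group at Month 3 (Group B) will be combined"; Group C stands alone.
- **Months 7–24:** three columns. Group A is merged with those who "are responders at Month 6 and continue to receive Elagolix 150 mg QD (Group E) will be combined"; Groups D and C each stand alone.

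No other safety section brings Group B back. Section 8.1.5.2 says: "Frequencies and percentages of subjects with TEAEs will be calculated for each treatment group as follows". It does not name the groups. Section 8.1.5.3 leaves laboratory data and vital signs to the SAP. Section 5.3.4 lists BMD as a safety variable ("BMD assessments will be summarized"). Section 8.1.5.4 names no groups for it and, unless specified elsewhere, "no statistical comparisons on BMD assessment will be performed between treatment groups". Sections 8.1.5.5 and 8.1.5.6 also name no groups.

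Under Section 5.1 only B and C are randomized, in equal ratio. Group A is defined by response at Month 3. It also receives subjects with no pain-score diary entries in the Month 3 window, who "will continue dosing with 150 mg QD for the remainder of the treatment period (will be assigned to Group A").

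**The concern.** From Month 3 to Month 6, B versus C is the only contrast created by randomization in which the two arms are wholly on different regimens. At Month 6, Group B is split by response and part of it moves to the regimen that C receives. Months 4–6 are therefore when a randomized view of adverse events is cleanest.

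The planned display does not give that view. A reader who sets the 150 mg column beside Group C compares a column made up mostly of Month 3 responders with a group made up entirely of incomplete responders. Any difference mixes regimen with responder selection, and no planned column separates the two. The plan treats efficacy differently: Sections 8.1.1, 8.1.4.1 and 8.1.4.2.1 compare B with C directly. The merging of B into A is particular to safety.

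**Working it through.** **Inputs.** From Section 8.3: 890 enrolled, 50% responders at Month 3, equal randomization of the rest, 80% of Group B switched at Month 6, 25% completion. Assumed here: everyone reaches Month 3.

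**Group sizes.** A = 890 × 0.5 = 445. B = C = 890 × 0.5 × 0.5 = 222.5. E = 0.2 × 222.5 = 44.5.

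**The plan's own figures.**
- Completers on 150 mg: 0.25 × (445 + 44.5) = 122, which agrees with the stated minimum of 120.
- Power for 20% versus 50% with 222.5 per arm, two-sided 0.05: (0.30 × √222.5 − 1.96 × √(2 × 0.35 × 0.65)) / √(0.16 + 0.25) = 4.92, so power exceeds 99.9%. This agrees with the stated figure of more than 90%.

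**Make-up of the pooled column.** A + B = 667.5, and A/(A + B) = 445/667.5 = 66.7%.
- A common dropout rate before Month 3 leaves this unchanged. At an assumed 30%, it is 311.5/467.25 = 66.7%.
- If a fraction z has no Month 3 diary entries and goes to A, then A = z + 0.5(1 − z) and B = 0.25(1 − z) as fractions of subjects. The share becomes 68.9% at an assumed z of 5% and 71.0% at 10%.

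**Effect on the comparison.** With rates a, b and c in the three groups, the pooled rate is (2a + b)/3. Hence (C − pool) − (C − B) = b − (2a + b)/3 = (2/3)(b − a). Illustrations with assumed rates:

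| A | B | C | Pool | C − pool | C − B |
|---|---|---|---|---|---|
| 10% | 10% | 10% | 10.0% | 0 | 0 |
| 10% | 20% | 20% | 13.3% | +6.7 points | 0 |
| 20% | 10% | 10% | 16.7% | −6.7 points | 0 |

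**Precision of a separate B column.** The 95% half-width for a risk difference is 1.96 × √(p(1 − p)(1/n₁ + 1/n₂)). Event rates p are assumed.

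| Comparison | p = 10% | p = 20% | p = 30% |
|---|---|---|---|
| C v B, 222.5 each | 5.6 | 7.4 | 8.5 |
| C v B, 155.75 each (assumed 30% dropout) | 6.7 | 8.9 | 10.2 |
| C v A+B, 222.5 v 667.5 | 4.6 | 6.1 | 7.0 |

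At full retention the ratio of C v B to C v A+B is √(2/222.5) / √(1/222.5 + 1/667.5) = √1.5 = 1.22, so the interval is about 22% wider.

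**The case against.** The best defence is that nothing planned is wrong. Pooling by regimen follows the protocol's own framework: Section 5.5.1 lists A and B under one 150 mg regimen, Section 8.1.2 analyses subjects by assigned regimen, and enrolment in Section 8.3 is sized on exposure to 150 mg. The BMD objective in Section 4.0 does not call for a randomized contrast. All of this stands, and it is why the pool should remain.

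Second, details are deferred to a SAP whose text is not in the supplied document, and the phrase about each treatment group in Section 8.1.5.2 could be read as A, B and C separately, as Section 5.1 labels them. This limits the finding to the supplied text but does not remove it. Section 8.1.5.1 states the Months 4–6 columns as a rule, and a SAP that followed it would reproduce the omission.

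Third, no safety difference between A and B is documented. One route to such a difference is largely closed: under Section 6.1.1.1, worsening endometriosis pain is not an adverse event unless serious. Moreover, assumed A–B differences of 3, 6 or 9 points shift the comparison by only 2, 4 or 6 points. Those shifts lie inside the C v B half-widths at full retention in every pairing except 6 points at a 10% event rate. This also stands. The added column would rarely prove that pooling distorted anything; its value is that it shows the randomized comparator.

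Two stronger readings are tempting. A reader might infer that the plan's safety comparison is biased. The documents do not support this: safety is descriptive by default and no test of C against the pool is planned. A reader might also infer that Month 6 BMD is expressly pooled. It is not. That grouping is inferred from Section 8.1.5.1, because Section 8.1.5.4 names no groups, and its key timepoints are Months 12 and 24.

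**Conclusion.** The point holds as a minor gap in presentation. In the supplied text the randomized 150 mg arm is never shown on its own beside Group C for safety, although Months 4–6 are when that contrast is intact.

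The firm figure is the make-up of the pooled column: about two thirds Group A on the inputs of Section 8.3, assuming full (or equal) retention to Month 3, and slightly more if some subjects enter Group A through missing diaries. It follows that two thirds of any A–B difference carries into a comparison of C with the pool. How large that difference is, and its sign, cannot be known from the documents; it may be zero. The event rates and half-widths above are illustrations only. No planned test, error rate or stated objective is affected.

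**What to change.** Keep the A+B column as the summary of exposure to 150 mg. In Section 8.1.5.1, add Group B as its own column beside Group C for Months 4–6, and carry it through the adverse-event and other safety summaries. Include a descriptive summary of Month 6 BMD percent change by randomized group, with the number scanned in each arm and no hypothesis test. The number scanned matters because Section 5.3.1.1 requires a discontinuation scan for "Subjects who discontinue prior to the Treatment Month 6 visit only if the reason for premature discontinuation is due to" a fracture or a newly diagnosed bone condition, so most early leavers will have no Month 6 value.

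The cost is a few extra table columns, from data already collected. An interval for C versus B would be about 22% wider than one for C versus the pool. Month 6 BMD reflects only about three months of differing treatment, so the addition supplements the 24-month BMD objective and does not answer it.

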8.1.5.2 Adverse Events

Adverse events (AEs) will be coded using the Medical Dictionary for Regulatory Activities (MedDRA) dictionary. Treatment-emergent adverse events (TEAEs) will be summarized. TEAEs are defined as AEs with a start date on or after the first dose of the study drug and within 30 days of the last dose of the study drug. AEs starting more than 30 days following discontinuation of the study drug will not be included in the summaries of TEAEs.

Frequencies and percentages of subjects with TEAEs will be calculated for each treatment group as follows:

- Any event
- By system organ class, and preferred term
- By system organ class, preferred term and maximum relationship
- By system organ class, preferred term and maximum severity
- Any event and by system organ class and preferred term for events resulting in study drug discontinuation
- Any event and by system organ class and preferred term for serious events
- Any event and preferred term for AESIs (e.g., hypoestrogenic adverse events)

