8.3 Determination of Sample Size

This study plans to enroll approximately 890 subjects to ensure a sufficient number of subjects receive elagolix 150 mg QD for 24 months.

Assuming the efficacy responder rate for the Daily Diary endometriosis-associated pain score via NRS is 50% during the open label elagolix 150 mg QD group at Month 3, 50% of subjects who complete Month 3 of the open-label period and are incomplete responders to 150 mg QD will be randomized in equal ratio to 150 QD and 200 BID plus E2/NETA.

Among those, assuming Month 6 DYS and NMPP responder rates of 20% for subjects who are randomized to elagolix 150 mg QD group (Group B) and 50% for subjects who are randomized elagolix 200 mg BID plus E2/NETA treatment group (Group C), this sample size provides greater than 90% power to detect a difference in response rate based on a 2-sided test at the significance level of $\alpha = 0.05$. The above sample size was calculated using nQuery advisor 7.0.

Assuming 80% of incomplete responders to 150 mg QD who are randomized to 150 QD at Month 3 are switched to elagolix 200 mg BID plus E2/NETA at Month 6 and a 25% completion rate, the current sample size will provide at least 120 subjects who receive elagolix 150 mg QD treatment group for 24 months (Group A and E).

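### Adverse events are specified as percentages within calendar blocks, with no table by time on regimen, so the Group C and Group D columns for Months 7–24 cover different stretches of the same treatment

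*Combined protocol and SAP*

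**What the plan says.** Section 8.1.5.1 (General Considerations, under Safety) sets three reporting blocks. The open-label run-in is summarized for all women together. Months 4–6 are shown for A and B combined and for C. For the last block, "For safety data collected during Treatment Months 7 – 24, summaries will be presented for the following group": A and E combined, D, and C. No statistical tests are planned unless otherwise specified, and analysis details are left to the SAP.

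Section 8.1.5.2 (Adverse Events) sets the measure: "Frequencies and percentages of subjects with TEAEs will be calculated for each treatment group as follows". Seven tabulations follow, and none uses person-time or time since the first dose of a regimen. TEAEs run from first dose of study drug to 30 days after the last dose. Nothing says how an event close to the Month 3 or Month 6 change of treatment is assigned to a regimen.

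Section 8.1.3 summarizes study drug exposure and premature discontinuations separately, without linking them to adverse events. Section 8.3 (Determination of Sample Size) assumes "a 25% completion rate" when counting women who finish 24 months on 150 mg QD.

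**The concern.** The synopsis and section 5.1 say the study evaluates the safety of both regimens over 24 months. A reader will want to know how often an event occurs after starting each regimen, and whether it occurs early or late. Calendar blocks answer that poorly here, because women start the combination at two different visits.

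Group C's first three months on the combination, and the women in C who leave during them, fall in the Months 4–6 table. Group D's first three months fall in the Months 7–24 table, beside C's later experience. If an event clusters soon after starting, D looks worse than C on the same drug. Section 8.1.5.2 names hypoestrogenic events as events of special interest and section 6.1.1.3 lists vasomotor symptoms; timing could plausibly matter for these.

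For 150 mg QD, one woman can be counted in up to three tables, and the denominators change between them. The block percentages therefore cannot be combined into a 24-month figure. Unequal drop-out adds a separate distortion to any crude percentage over 18 months.

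**Working it through.** **1. The plan's own figure.** From section 8.3: "This study plans to enroll approximately 890 subjects"; half respond at Month 3; the rest "will be randomized in equal ratio to 150 QD and 200 BID plus E2/NETA"; 80% of B switch at Month 6.

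- A = 890 × 0.50 = 445; B = C = 445 / 2 = 222.5
- D = 0.80 × 222.5 = 178; E = 222.5 − 178 = 44.5
- 24-month completers on 150 mg QD = (445 + 44.5) × 0.25 = 122.4, against the stated minimum of 120

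The figure reproduces. It also shows that the 25% is applied there to A and E only.

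**2. What each block covers.**

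| Block | 150 mg QD | Combination |
|---|---|---|
| Months 1–3 | all women | none |
| Months 4–6 | A + B | C, regimen months 1–3 |
| Months 7–24 | A + E | C, regimen months 4–21; D, regimen months 1–18 |

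**3. C against D with identical drug effects.** The documents give no event rates, so these inputs are assumptions: first-event risk p in the first three months on the combination, then risk q per 12 months, and the same exponential drop-out in both groups, l = ln(4)/24 = 0.0578 per month (25% remaining at Month 24).

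- a = −ln(1 − p)/3; b = −ln(1 − q)/12
- Crude(h, T) = h/(h + l) × [1 − exp(−(h + l)T)]
- D = Crude(a, 3) + exp(−3(a + l)) × Crude(b, 15)
- C = Crude(b, 18), among women event-free at Month 7

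For p = 10%, q = 5%: a = 0.0351, b = 0.00427. D = 9.2% + 0.757 × 4.17% = 12.4%. C = 4.6%.

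| p | q | D | C | D/C |
|---|---|---|---|---|
| 5% | 10% | 11.2% | 9.2% | 1.2 |
| 5% | 5% | 7.9% | 4.6% | 1.7 |
| 10% | 10% | 15.5% | 9.2% | 1.7 |
| 10% | 5% | 12.4% | 4.6% | 2.7 |
| 30% | 10% | 32.6% | 9.2% | 3.5 |
| 30% | 5% | 30.1% | 4.6% | 6.5 |

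The effect does not need drop-out. With none, D = 1 − (1 − p)(1 − q)^(15/12) and C = 1 − (1 − q)^(18/12). For p = 10%, q = 5% this gives 15.6% against 7.4%, a ratio of 2.1; over the table the ratio runs from 1.1 to 4.6. If the hazard is constant (a = b) and drop-out equal, the gap disappears.

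**4. Drop-out alone.** Take the same l and a constant hazard.

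- Share of Month 6 women remaining at Month 24: exp(−18 × 0.0578) = 0.354
- Mean time observed in the block: (1 − 0.354)/0.0578 = 11.2 of 18 months (11.8 if drop-out is linear from Day 1)
- For a true 18-month risk of 10%, h = −ln(0.9)/18 = 0.00585, and Crude(h, 18) = 6.3%
- Adding the 30-day TEAE tail (30/28 = 1.07 study months) to each woman's observation: about 6.9%
- Two groups with this hazard, keeping 50% and 25% from Month 6 to 24 (retention figures assumed): 7.3% and 5.5%, or 7.8% and 6.1% with the tail

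**5. Whether one person-time rate would cure this.** Let the 10% risk be front-loaded, with 8 points in the first three months (assumption). At 50% and 25% retention the crude percentages are 8.9% and 8.1%, a 9% relative gap. Single first-event rates are 8.9 and 10.8 per 100 women per 12 study months, a 21% gap in the opposite direction. A single rate can therefore be worse than the percentage; splitting by interval on regimen avoids this.

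**The case against.** Several stronger readings are tempting, and the documents do not support them.

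- A reader might infer that no exposure-adjusted or on-regimen table will be produced. Section 8.1.5.1 defers detail to the SAP, and no separate SAP text is in the supplied document. Section 8.1.2 also defines a double-blind analysis set covering Months 4–24 as a whole. All that can be said is that the protocol specifies none.
- A reader might infer that no table counts events from the first combination dose. For Group D, Months 7–24 is the entire planned exposure to the combination, so that column is a crude cumulative percentage from first dose. The statement is true of C only.
- A reader might infer that the plan expects 75% of all women to leave. The 25% is a sizing assumption used for A and E; extending it to C and D is extrapolation.
- A reader might infer a biased formal comparison of C with D. None is planned. The safety summaries are descriptive, and the listed safety objectives concern BMD, which is measured at fixed visits and is unaffected.

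It is also fair that the early-risk argument needs a changing hazard while the drop-out illustration uses a constant one; they are separate illustrations, not one model. The separate summaries of exposure and discontinuation would alert readers to unequal follow-up, but would not let them reconstruct risk by time on regimen.

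What survives is that sections 8.1.5.1 and 8.1.5.2 do fix both the blocks and the measure, and that together they place unlike periods of the same regimen side by side.

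**Conclusion.** The point holds as a gap in the specified descriptive reporting. The misalignment of C and D by three months on the combination follows directly from the design and does not depend on any drop-out figure. Its effect depends on how far events cluster early: a D-to-C ratio of 1.2 to 6.5 under the assumed risks with drop-out, 1.1 to 4.6 without, and none at a constant hazard with equal drop-out. The shortfall from drop-out, 10% appearing as about 6–7%, is an illustration resting on exponential drop-out, a constant hazard and a completion rate stated only for A and E.

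Even aligned by time on regimen, C and D would not be a randomized comparison. D is selected on non-response at Month 6 as well as Month 3, and reaches the combination after six months of 150 mg QD, not three.

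**What to change.** Keep the block tables and add to section 8.1.5.2, with matching SAP text:

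- **Main addition:** TEAE tables by regimen from the first dose of that regimen. For 150 mg QD, from Day 1 until switch or stop. For the combination, from the first combination dose, with C and D shown separately and pooled. State that each event is assigned to the regimen being taken at onset.
- **Alongside:** exposure-adjusted first-event rates for any TEAE, serious events, events leading to discontinuation, and events of special interest, shown by interval on regimen (for example the first three months, then later). A single overall rate should not stand alone, because it assumes a constant hazard.

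The cost is a few more descriptive tables from data already collected. Treatment, visits and sample size are unaffected.
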